5. STATISTICAL ANALYSES

5.1. General Considerations

A baseline (or reference) value will be defined as the value of the last available assessment prior to the first vaccination on Day 1, where Day 1 is the date of first vaccination for adults. A value at birth is baseline value for neonates and the birth date is the neonate reference date. The neonate baseline values for immunogenicity analysis are those from the cord blood sample collected.

Every adult will have a unique subject ID in the ADaM datasets and every neonate will have the same unique subject ID with 'A' added at the end of the ID. Multiple pregnancies [twins or higher order multiples] are excluded from the study but if a participant with multiple pregnancy is inadvertently enrolled, neonates will have the same unique subject ID with 'A', 'B', 'C' and D added at the end of the ID based on the number of neonates.

Unless otherwise specified, continuous variables will be summarized using the following statistics, as appropriate: number of observations, arithmetic mean (mean), standard deviation (SD), standard error (SE), median, minimum, and maximum. Frequencies and percentages (one decimal place) will be generated for categorical variables. Denominator for the percentages is the number of participants in the considered population, and phase (where applicable; incidence per 100 participants/phase).

No formal statistical testing is planned. The safety analysis will be performed on the FAS-A based on actual intervention received and the FAS-NVN, unless otherwise specified. Safety data will be presented by period/phase (as applicable) as well as over the entire study. Immunogenicity results will be conducted on the PPI-A and PPI-NVN and presented per scheduled time point as appropriate. Safety and immunogenicity endpoints will be summarized descriptively by previous vaccination group (as defined in Section 1.2) and overall. All listings will include the previous vaccination group. Vaccination schedule in Group 4 (i.e. vaccine-naive at study entry) will have two components: the Primary Vaccination and the (optional) Booster Vaccination. Listings will be shown per phase and time point, as appropriate.

Participants that took another COVID-19 vaccine during the study are excluded from all safety and immunogenicity analyses from the moment they received the other vaccine. The safety data from those participants after they received the other vaccine will be listed separately.

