follow-up 2'

max PN D183

(neonates); i.e. PN D43 to

	Phase		Period		Interval
Phase	#	Period	#	From	То
'Postnatal follow-up 3' (neonates); i.e. PN D183 to max PN D366	7			One minute after Postnatal follow-up 2 period ends	 Minimum of : g) Maximum of 23:59 at the date of last contact (for early discontinuation) and 23:59 at the date of last visit h) 23:59 at the date of data base cut-off date in case of interim analysis i) D366 after birth j) One minute before date and time of another COVID-19 vaccination outside the study k) One minute prior to end of the study visit
'Post-dose' (Booster)	2	Post-dose 2 (i.e. Post- Booster)	2	Date and time of second vaccination (i.e. Booster)	 Minimum of: a) 23:59 at the date of last contact (for early discontinuation) b) 23:59 at the date of data base cut-off date in case of interim c) 23:59 on 28 days after the Booster Vaccination (23:59 of that day + 28 days) d) One minute before date and time of another COVID-19 vaccination outside the study
Booster follow-up 1	8			One minute after post-dose 2 period ends	 Minimum of: a) 23:59 at the date of last contact (for early discontinuation) b) 23:59 at the date of data base cut-off date in case of interim c) One minute prior to 6 months after Booster Vaccination d) One minute before date and time of another COVID-19 vaccination outside the study
Booster follow-up 2	9			One minute after Booster follow-up 1	 Minimum of: a) Maximum of 23:59 at the date of last contact (for early discontinuation) and 23:59 at the date of last visit b) 23:59 at the date of data base cut-off date in case of interim c) One minute before date and time of another COVID-19 vaccination outside the study e) One minute prior to end of the study visit
Follow-up other vaccine	10			Date and time of viral vaccination outside the study	 Minimum of: a) Maximum of 23:59 at the date of last contact (for early discontinuation) and 23:59 at the date of last visit b) 23:59 at the date of data base cut-off date in case of interim analysis c) Date and time of end of the study visit

Note: PP Dx = Postpartum Day x, PN Dx = Postnatal Day x

Adverse Events (AE) tables and selected other tables may display AEs (or other counts) by phase. For such tables, post vaccination periods can be combined and additionally displayed. The "active" periods can be defined as:

- "Post-Dose 1"
- "Post-Booster", where applicable (booster)
- "Post-Dose 1 and Post-Booster Combined", where applicable.

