5.3. Primary Endpoint(s) Analysis

5.3.1. Definition of Endpoints

Safety and reactogenicity of Ad26.COV2.S (first vaccination) in adult participants

- Solicited local and systemic AEs for 7 days after (first) vaccination, or until resolution
- Unsolicited AEs for 28 days after (first) vaccination
- SAEs and AESI throughout the study (from first vaccination until end of the study, i.e. at least 12 months after delivery)
- MAAEs until 6 months after the last vaccination
- AEs leading to study discontinuation (during the entire study)

Refer to Sections 5.6.1 for more details on adverse events definitions.

Humoral Immune Response in peripheral blood of adult participants

• Serological response to vaccination as measured by enzyme-linked immunosorbent assay (ELISA; [S-ELISA, EU/mL]), 28 days after vaccination

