5.4.3. Analysis Methods

Safety and reactogenicity of Ad26.COV2.S (incl Pregnancy-related AEs)

The secondary safety and reactogenicity endpoints for adult participants and neonates/infants (separately) of the study will be evaluated with AEs, SAEs, AESIs and MAAEs as detailed in Section 5.6.1 for definitions and analyses methods of adverse events.

Key analyses will also be performed by subgroup: gestational age group, participant age group at baseline, and the SARS-CoV-2 serostatus at baseline. Refer to Section 5.7.5 for subgroup definitions.

Refer to Section 6.8 for Pregnancy-related AEs.

Outcomes

The frequency and percentage of participants (adult participants, and neonates/infants, separately) for whom at least one of the indicated outcomes was reported will be reported. For each separate maternal/fetal and neonatal/infant outcome, the number and percentage of participants who experience at least 1 occurrence of the given outcome will also be tabulated. Denominator for the percentages is the number of participants in the considered population and phase (incidence per 100 participants/phase).

Outcomes will be presented by phase (Post-dose 1, Post-booster, Postpartum Follow-up 1, etc., as applicable), as well as over the entire study and follow-up periods. Outcomes may also be presented by subgroup: gestational age group, participant age at screening, and SARS-CoV-2 serostatus at baseline.

Denominator for the percentages is the number of participants in the considered population and phase (incidence per 100 participants/phase).

Humoral Immune Response in peripheral blood of adult participants

Refer to Section 5.7.1 for definitions and analyses methods of immunogenicity endpoints.

Antibody levels against SARS-CoV-2 in neonates/infants

Refer to Section 5.7.1 for definitions and analyses methods of immunogenicity endpoints.

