5.6.1.3. Analysis of Adverse Events

Solicited AEs (shown in output) are extracted from the investigator assessment pages of the CRF and will be recorded in the Clinical Event SDTM domain. Only Solicited AEs with onset within 7 days after vaccination (post-dose 1, post-booster [booster in Group 4], and post-dose 1+ post-booster) will be reported in tables. For unsolicited AEs, only the AEs within the 28-day period following (primary or booster) vaccination will be presented in the safety tables except for SAEs, AEs leading to treatment/study discontinuation (incl. MAAE leading to treatment/study discontinuation) and AESIs which will be captured and tabulated in the outputs covering the whole study period (i.e. up to 12 months postpartum), and MAAEs which will be captured and tabulated for all participants from the first vaccination until 6 months after (each) vaccination.

Number and percentage of participants with at least one particular AE (unsolicited/solicited) will be tabulated. Unsolicited AEs will be summarized by System Organ Class and Preferred Term. Solicited AEs will be summarized by class (administration site/systemic) and Preferred Term.

For solicited AEs following tables will be provided: summary, by worst severity grade, at least grade 3, related (systemic only), time to onset (in days) and duration (in days) for most frequent events (>5%) and body temperature. Note: Duration is defined as number of days from the start of the event until resolution of the event. The time to first onset is defined as (date of first onset – reference date + 1). The reference date is the start date of the vaccination period.

For unsolicited AEs, the following tables will be provided: summary table (including SAE, AESI, MAAEs, AEs leading to treatment/study discontinuation, fatal outcome, and discontinuation), all events, most frequent (>5%), at least grade 3, related, and SAEs. The proportion of AEs resulting in a medically attended visit (other than routine health maintenance visits) will also be tabulated.

Pregnancy-related AEs in adult participants (including gestational diabetes, gestational hypertension, premature rupture of membranes, premature labor, premature uterine contractions, poor or restricted fetal growth, pre-eclampsia, eclampsia, vaginal or intrauterine hemorrhage [non-exhaustive]) will be tabulated separately. The complete list of preferred terms to be included as pregnancy related AEs is provided in Section 6.8.

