5.7. Other Analyses

5.7.1. Immunogenicity

The PPI-A set will be used for analysis of immunogenicity for adult participants and the PPI-NVN set will be used for neonates/infant.

Selected immunogenicity analyses will also be done on the FAS-A and FAS-NVN. Participants who become infected during the study or receive another COVID-19 vaccine outside of the study will be analyzed as subgroups and identified in graphs using specific colors and symbols. Data will be analyzed separately for adult participants and for neonates/infants.

Key immunogenicity assay data from other studies may be used in selected graphs and tables, for descriptive comparison of immunogenicity results in pregnant women from COV2004 vs non-pregnant women in other Janssen Ad26.COV2.S studies. Reference to the respective study will be added and clearly indicated in those tables and graphs.

Key immunogenicity assay results (S-ELISA, VNA) will also be analyzed for the subgroups defined in Section 5.7.4.

CONFIDENTIAL – FOIA Exemptions Apply in U.S.

Data will be presented by scheduled time point. For inclusion of immunogenicity samples taken outside of the allowed windows, see section 5.1.3. For the FAS-A and FAS-NVN analyses, samples taken outside of the allowed window will be included.

Categorical variables will be summarized with a frequency table showing counts and percentages. Continuous variables will be summarized using the following statistics, as appropriate: number of observations, geometric mean, 95% confidence interval (CI) for geometric mean, arithmetic mean (mean), 95% CI for the mean, standard deviation (SD), standard error (SE), median, quartiles (Q1 andQ3), minimum and maximum.

Data listings, participant profiles and/or participant narratives may be provided as appropriate. Binary variables will be summarized using the following statistics: number of observations, percentages, and Exact Clopper-Pearson 95% CIs.

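### SAEs and AESIs that follow another COVID-19 vaccine leave the whole-study safety tables, against the SAP's own primary endpoint; the SAP is unclear whether pregnancy outcomes go with them

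*SAP*

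**What the plan says.** **The cut-off.** Section 5.1: "Participants that took another COVID-19 vaccine during the study are excluded from all safety and immunogenicity analyses from the moment they received" that vaccine. It then adds: "The safety data from those participants after they received the other vaccine will be listed separately".

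**How it is built in.** In Table 3 (Section 5.1.2) the post-dose, prepartum, postpartum/postnatal and booster phases each stop one minute before a COVID-19 vaccination outside the study. Later time goes to Phase 10, whose start is given as "Date and time of viral vaccination outside the study". Table 4 (Section 5.1.2.1) ends the Entire Study interval at the later of the primary and booster period ends. Both periods are assembled from the truncated phases, and Phase 10 appears in neither.

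**What is promised.** Section 5.3.1 lists among the primary endpoints "SAEs and AESI throughout the study (from first vaccination until end of the study, i.e. at least 12 months after delivery". Section 5.6.1.3 says that SAEs, AESIs and AEs leading to discontinuation "will be captured and tabulated in the outputs covering the whole study period (i.e. up to 12 months postpartum".

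**Pregnancy outcomes.** Section 5.4.3 tabulates them by phase and over the whole study: "Denominator for the percentages is the number of participants in the considered population and phase (incidence per 100 participants/phase". Section 5.8.2 gives them as an example of safety data. Section 4 names them beside safety and immunogenicity, as a category of their own.

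**Immunogenicity.** Section 5.7.1 says that participants who "receive another COVID-19 vaccine outside of the study will be analyzed as subgroups".

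**The concern.** The primary safety question is what happens to women dosed in pregnancy up to about a year after delivery. A rule that stops counting when a woman takes another product answers a narrower question: what happens until then. That can be a legitimate choice, but the SAP does not declare it. Section 5.3.2 sets the estimand to not applicable, the endpoint still runs to end of study, and no planned safety table keeps the later events.

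The study has no control arm, so the tabulated rates will be read at face value. Rare late events are the ones most easily lost, and one event in 240 is 1/240 = 0.42%, just below the lowest rate in the SAP's Table 1 (0.5%).

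**Working it through.** **1. Trace one woman through the tables.** Take a woman who has the study vaccine, then another COVID-19 vaccine, then an SAE.

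- *Phase tables.* Her current phase closes one minute before the other vaccine. The SAE has a later start, so under Section 5.6.1.4 it is allocated to Phase 10.
- *Entire Study.* Table 4 takes the latest end date among the truncated phases. The SAE falls after it.
- *Output.* Section 5.1 sends the SAE to the separate listing. No whole-study table holds it, although Sections 5.3.1 and 5.6.1.3 both require one.

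If the other vaccine comes before delivery, Postpartum follow-up 1 starts at birth but has to end before birth. The phase is empty, so a delivery tabulated by phase has no place except Phase 10.

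**2. The denominator.** In by-phase tables the denominator counts participants in the population and phase, so a woman with no postpartum phase leaves numerator and denominator together. The whole-study denominator is less clear. She meets the FAS-A definition, her Entire Study interval has begun, and nothing in Section 5.1 removes her from the count. The nearest rule, in Section 5.6.1.5, treats participants without a reported event as event-free. If she stays in the denominator, her later SAE is in effect scored as no event.

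**3. The plan's own figures.** Section 3 gives upper limits after zero events and, in Table 1, the chance of seeing at least one event.

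- Zero-event two-sided 95% limit, 1 − 0.025^(1/N): 8.81%, 5.96%, 3.03% and 1.53% for N = 40, 60, 120 and 240. The SAP states 8.8%, 6%, 3% and 1.5%.
- Chance of at least one event, 1 − (1 − p)^N, with N = 240: 70.0% at p = 0.5% and 91.0% at p = 1.0%. The SAP states 70% and 91%.

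All 28 cells of Table 1 reproduce. They describe complete counting of events.

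**4. Illustration of the loss.** The SAP gives neither of two quantities needed here, so both are assumed:

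- f, the share of women who take another vaccine: 5% to 30%
- g, the share of those women's event risk that falls after it: 25% to 100%

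With the denominator kept at all FAS-A women, the tabulated rate is p × k, where k = 1 − f × g. At the mild end k = 1 − 0.05 × 0.25 = 0.9875. At the severe end k = 1 − 0.30 × 1.00 = 0.70.

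| Quantity | Full counting | k = 0.9875 | k = 0.70 |
|---|---|---|---|
| Tabulated rate, true 2.0% | 2.00% | 1.98% | 1.40% |
| Chance of at least one tabulated event, true 1.0%, N = 240 | 91.0% | 90.8% | 81.5% |
| Same, true 0.5%, N = 240 | 70.0% | 69.5% | 56.9% |

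The second and third rows are 1 − (1 − p × k)^240. The 240 is the enrolment target. Section 3 says that enrolment has ceased and gives no final number.

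**5. Related wording.**

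- Phase 10 opens at any viral vaccination, while the other phases close only at a COVID-19 vaccination. Read literally, a non-COVID viral vaccine puts a woman in two phases at once.
- The first postpartum row of Table 3 serves adults and neonates alike, and the neonate-only Phase 7 carries the same stop. Neither says whose vaccination is meant, and FAS-NVN has no such exclusion.
- Section 5.1 bars these women from all immunogenicity analyses after the other vaccine, while Section 5.7.1 analyses them as a subgroup.

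**The case against.** The best defence is that stopping at a second product is a recognised choice in a descriptive study with no hypothesis, and that nothing is hidden. Later safety data are listed, women with another vaccine are counted in disposition (Section 5.2), Section 5.6.1.3 provides listings or narratives for deaths and SAEs, and Phase 10 exists to hold the later time. That is fair, and it limits the harm: the events remain visible. It does not restore the whole-study rates, and it does not reconcile the cut-off with the endpoint definition.

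Three stronger readings are tempting, and the SAP does not support them.

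- *Deliveries are certainly lost.* Sections 5.8.2 and 5.4.3 point that way. But Sections 2 and 4 set pregnancy outcomes apart from safety, and Section 5.6.3 says that delivery history will be summarised, with no exclusion. The loss is probable, not established, and arises only if the other vaccine came first.
- *A stated number of deliveries goes missing.* Assuming that 5% to 20% of 240 women are vaccinated elsewhere before delivery gives 240 × 0.05 = 12 to 240 × 0.20 = 48. No figure in the SAP informs that share, and 240 is a target for an enrolment that has stopped.
- *Pregnancy risk is understated throughout.* Longer pregnancies allow more time for another vaccine, so late deliveries would be lost more often. Among the outcomes observed, that would tend to overstate the preterm share. Understatement is supported for late SAEs and AESIs, and only if the denominator stays at FAS-A.

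The viral-vaccination wording may be no more than loose drafting, since the row is named for the other vaccine. It is still worth correcting.

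**Conclusion.** The point holds for SAEs and AESIs. The cut-off in Section 5.1, carried through Tables 3 and 4, contradicts Sections 5.3.1 and 5.6.1.3. Following it as written drops events after another COVID-19 vaccine from the whole-study tables. The rates are understated on condition that these women remain in the whole-study denominator, which the SAP implies but does not state.

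For pregnancy outcomes the finding is an ambiguity that needs settling. Neither the size nor the direction of any effect on their proportions can be determined from the SAP. The figures in the illustration show scale under assumed inputs and are not estimates. At the mild end the effect is negligible; at the severe end a true 2.0% rate loses 0.6 percentage points (2.00% − 1.40%).

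This should be corrected before the analysis.

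**What to change.** - **Section 5.1.** Limit the cut-off to immunogenicity, solicited AEs and 28-day unsolicited AEs. Keep SAEs, AESIs, pregnancy outcomes, pregnancy-related AEs and neonate/infant outcomes in the whole-study FAS-A and FAS-NVN tables whether or not another vaccine was taken, with a flag on events that follow one. AEs leading to discontinuation share the Section 5.6.1.3 promise and should follow the same rule.
- **Sensitivity.** Give the version cut at the other vaccine as a sensitivity table.
- **Table 4.** Include Phase 10 in Entire Study, and state the denominator of the whole-study tables.
- **Table 3.** Start Phase 10 at another COVID-19 vaccination instead of any viral vaccination, and say whose vaccination ends the postnatal phases.
- **Section 5.7.1.** Reconcile the subgroup analysis with Section 5.1, for example by confining the exclusion to the per-protocol sets.

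The cost is SAP wording and a second version of a few tables, since the later safety data are already to be listed. The drawback is that some retained events will follow a second product and may be due to it; the flag and the sensitivity table let the reader see how many.

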5.1.1. Study Phases

To assess study phases, in case the time of the vaccination is missing, the time will be imputed with 00:00 before applying the phase and period derivation rules.

5.1.2. Phase Definitions

The phases in the study will be constructed as detailed in Table 3 below.

post partum for adults

e)

f)

d) One minute prior to date and time of

Booster Vaccination (if applicable)

One minute before date and time of another

COVID-19 vaccination outside the study One minute prior to end of the study visit

Table 3: P	hase Defi	nitions			
	Phase		Period		Interval
Phase	#	Period	#	From	То
Screening	1	Screening		Date and time of signing the informed consent form	One minute prior to start of Post-dose 1 period
Post-dose	2	Post-dose 1	1	Date and time of first vaccination	 Minimum of: a) 23:59 at the date of last contact (for early discontinuation) b) 23:59 at the date of data base cut-off date in case of interim analysis c) 23:59 on 28 days after the first vaccination (23:59 of day of vaccination + 28 days) d) One minute prior to date and time of Booster Vaccination e) One minute before date and time of another COVID-19 vaccination outside the study f) One minute prior to neonatal/infant birth or pregnancy termination
Prepartum follow-up 1	3			One minute after Post-dose 1 period end	 Minimum of: a) 23:59 at the date of last contact (for early discontinuation) b) 23:59 at the date of data base cut-off date in case of interim c) One minute prior to 6 months after first vaccination (vaccination date + 6 mths) d) One minute prior to date and time of Booster Vaccination (if applicable) e) One minute before date and time of another COVID-19 vaccination outside the study f) One minute prior to neonatal/infant birth or pregnancy termination
'Postpartum follow-up 1' (adults) and 'Postnatal follow-up 1' (neonates); i.e. PP/PN D1 up to max PP/PN D42	5			Neonatal/infant birth or pregnancy termination	 Minimum of: a) 23:59 at the date of last contact (for early discontinuation) b) 23:59 at the date of database cut-off date in case of interim analysis c) 42 days after the neonate birth date d) One minute prior to date and time of Booster Vaccination (if applicable) e) One minute before date and time of another COVID-19 vaccination outside the study
'Postpartum follow-up 2' (adults); i.e. PP D43 to max PP D366 'Postnatal	6			One minute after postpartum follow-up 1/ Postnatal follow-up 1 period ends	 Minimum of : a) Maximum of 23:59 at the date of last contact (for early discontinuation) and 23:59 at the date of last visit b) 23:59 at the date of data base cut-off date in case of interim analysis c) D183 after birth for neonates and D366

follow-up 2'

max PN D183

(neonates); i.e. PN D43 to

	Phase		Period		Interval
Phase	#	Period	#	From	То
'Postnatal follow-up 3' (neonates); i.e. PN D183 to max PN D366	7			One minute after Postnatal follow-up 2 period ends	 Minimum of : g) Maximum of 23:59 at the date of last contact (for early discontinuation) and 23:59 at the date of last visit h) 23:59 at the date of data base cut-off date in case of interim analysis i) D366 after birth j) One minute before date and time of another COVID-19 vaccination outside the study k) One minute prior to end of the study visit
'Post-dose' (Booster)	2	Post-dose 2 (i.e. Post- Booster)	2	Date and time of second vaccination (i.e. Booster)	 Minimum of: a) 23:59 at the date of last contact (for early discontinuation) b) 23:59 at the date of data base cut-off date in case of interim c) 23:59 on 28 days after the Booster Vaccination (23:59 of that day + 28 days) d) One minute before date and time of another COVID-19 vaccination outside the study
Booster follow-up 1	8			One minute after post-dose 2 period ends	 Minimum of: a) 23:59 at the date of last contact (for early discontinuation) b) 23:59 at the date of data base cut-off date in case of interim c) One minute prior to 6 months after Booster Vaccination d) One minute before date and time of another COVID-19 vaccination outside the study
Booster follow-up 2	9			One minute after Booster follow-up 1	 Minimum of: a) Maximum of 23:59 at the date of last contact (for early discontinuation) and 23:59 at the date of last visit b) 23:59 at the date of data base cut-off date in case of interim c) One minute before date and time of another COVID-19 vaccination outside the study e) One minute prior to end of the study visit
Follow-up other vaccine	10			Date and time of viral vaccination outside the study	 Minimum of: a) Maximum of 23:59 at the date of last contact (for early discontinuation) and 23:59 at the date of last visit b) 23:59 at the date of data base cut-off date in case of interim analysis c) Date and time of end of the study visit

Note: PP Dx = Postpartum Day x, PN Dx = Postnatal Day x

Adverse Events (AE) tables and selected other tables may display AEs (or other counts) by phase. For such tables, post vaccination periods can be combined and additionally displayed. The "active" periods can be defined as:

- "Post-Dose 1"
- "Post-Booster", where applicable (booster)
- "Post-Dose 1 and Post-Booster Combined", where applicable.

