5.1.2.1. Other time intervals

The following other time intervals will be derived for safety data summary as shown in Table 4.

Time Intervals	From	То
Up to Postpartum Day43	Date and time of first	Maximum of:
	vaccination	a) Post-dose 1 end date
		b) Prepartum follow-up 1 end date
		c) Postpartum follow-up 1 end date
Primary Vaccination Period	Date and time of first	Maximum of:
(in vaccine naïve group only)	vaccination	a) Post-dose 1 end date
		b) Prepartum follow-up 1 end date
		c) Postpartum follow-up 1 end date
		d) Postpartum follow-up 2 end date
Booster Vaccination Period	Date and time of Booster	Maximum of:
(in vaccine naïve group only)	Vaccination	a) Post-dose 2 end date
		b) Post Booster follow-up 1 end date
		c) Post Booster follow-up 2 end date
Entire Study	Date and time of first	Maximum of:
	vaccination	a) Primary Vaccination Period end date
		b) Booster Vaccination Period end date

Table 4:Other Time Intervals

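### Table 3 ends Post-dose 1 at delivery, in unreconciled conflict with the 28-day unsolicited-AE window of the primary safety endpoint

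*SAP*

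**What the plan says.** Section 5.1.2, Table 3, ends Post-dose 1 at the minimum of six times. The nominal end is rule (c), "23:59 on 28 days after the first vaccination (23:59 of day of vaccination + 28 days". Rule (f) is "One minute prior to neonatal/infant birth or pregnancy termination". Postpartum follow-up 1 then starts at "neonatal/infant birth or pregnancy termination". After the first dose, Post-dose 1 is the only period that Section 5.1.2 calls active.

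Section 5.3.1 defines the primary endpoint component as "Unsolicited AEs for 28 days after (first) vaccination". Section 5.6.1.3 says that, for unsolicited AEs, "only the AEs within the 28-day period following (primary or booster) vaccination will be presented in the safety tables", with listed exceptions that have longer windows. Neither section mentions delivery.

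Section 5.1 says "Safety data will be presented by period/phase (as applicable) as well as over the entire study" and sets percentages per participant in the population and phase. Section 5.6.1.4 allocates AEs to periods by start date and time. For pregnancy and neonatal outcomes, Section 5.4.3 says "Outcomes will be presented by phase (Post-dose 1, Post-booster, Postpartum Follow-up 1, etc., as applicable".

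Table 4 (Section 5.1.2.1) has an interval from first vaccination to the end of Postpartum follow-up 1, but no fixed 28-day interval. Its Entire Study interval ends at the later of two dates, the first being "a) Primary Vaccination Period end date". Both component periods are labelled as applying to the vaccine-naïve group only.

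**The concern.** The primary safety window has two definitions, and the SAP does not say which one the 28-day tables use. Two programmers following it could produce different primary tables.

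If Post-dose 1 is used, a new unsolicited AE that starts after a delivery within 28 days of vaccination falls in Postpartum follow-up 1, which is non-active. The woman stays in the Post-dose 1 denominator as one participant, so nothing reflects her shorter observation. Safety is also summarised by gestational-age group (Sections 5.3.3 and 5.7.5), and the cut falls almost wholly on the later stratum, so the two strata would be described over unequal windows.

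For outcomes, the phase that contains a timed birth or loss begins at that event. A zero in the Post-dose 1 outcome column would therefore follow from the definition, yet could be read as a safety result.

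**Working it through.** The plan states no figure on this point, so there is none to reproduce. The check applies the Table 3 rules to a dated example and then asks who is affected.

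**Step 1: the rules on one case.** Take vaccination on 1 March at 10:00 and birth on 15 March at 14:30.

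- Rule (c): 1 March 23:59 + 28 days = 29 March 23:59.
- Rule (f): 15 March 14:30 − 1 minute = 15 March 14:29.
- Post-dose 1 end = min(29 March 23:59, 15 March 14:29) = 15 March 14:29, so 14 of 28 days are kept.
- The birth at 14:30 is outside Post-dose 1 and inside Postpartum follow-up 1.
- A new unsolicited AE on 20 March is within 28 days under Sections 5.3.1 and 5.6.1.3, but outside Post-dose 1.
- Prepartum follow-up 1 would start at 14:30 and end at 14:29, so it is empty.

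**Step 2: events without a time.** Section 5.6.1.4 matches partial dates on what is available and allows assignment to several periods. An event dated 15 March with no time matches both Post-dose 1 and Postpartum follow-up 1, so it can count in Post-dose 1. With a birth at 00:00, Post-dose 1 ends the day before and the match fails.

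**Step 3: length of the window.** Days kept = min(28, gestational age at delivery − gestational age at vaccination), in days. Vaccination at 38+0 with delivery at 40+0 keeps 14 days; vaccination at 38+6 keeps 8.

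**Step 4: who is cut.** Enrolment runs from week 16 to week 38 (Section 1.2), with strata split at week 28. Assumptions, not in the SAP: vaccination is spread evenly by day over the span, and all deliveries occur at one gestational age, varied from 37+0 to 41+0. Week 38 is read both as ending at 38+0 and at 38+6. Share cut = vaccination days from which delivery follows within 28 days ÷ vaccination days before delivery. Delivery on day 28 itself is counted as cut.

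| Delivery at | 28-38 weeks, to 38+0 | 28-38 weeks, to 38+6 | 16-38 weeks, to 38+0 | 16-38 weeks, to 38+6 |
|---|---|---|---|---|
| 37+0 | 28/63 = 44.4% | 28/63 = 44.4% | 28/147 = 19.0% | 28/147 = 19.0% |
| 39+0 | 22/71 = 31.0% | 28/77 = 36.4% | 22/155 = 14.2% | 28/161 = 17.4% |
| 40+0 | 15/71 = 21.1% | 21/77 = 27.3% | 15/155 = 9.7% | 21/161 = 13.0% |
| 41+0 | 8/71 = 11.3% | 14/77 = 18.2% | 8/155 = 5.2% | 14/161 = 8.7% |

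The range is about 11-44% of the 28-38 week stratum and 5-19% of the whole span. Women who are cut keep on average 14.5 days (delivery at 37+0) to 24.5 days (delivery at 41+0, vaccination up to 38+0).

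**Step 5: the earlier stratum.** The latest vaccination in it is at 27+6, and 27+6 plus 28 days is 31+6. Only a delivery or termination by then can cut the window.

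**The case against.** The strongest reply is that Sections 5.3.1 and 5.6.1.3 still state 28 days, and that by-phase display is qualified as applicable. A reader might infer that the plan removes post-delivery AEs from the primary 28-day table. The document does not establish that: nowhere does it say that rule (f) governs that table. This stands, and it makes the fault a conflict between sections, not a proven redefinition of the endpoint. The Data Presentation Specifications might settle it, but the primary endpoint's window should be fixed in the SAP.

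A reader might also infer that no pregnancy loss or preterm birth could ever be counted in Post-dose 1, or that the plan would report none within 28 days. Neither follows. An event with no time can match Post-dose 1 (Step 2), and an AE with onset before delivery, such as premature labor, belongs there by its start date. Section 5.4.3 plans no 28-day outcome table, and a birth or loss remains visible in the postpartum phase and over the entire study.

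The safeguards are real. Solicited AEs always go to the post-dose period. SAEs, AESIs and AEs leading to discontinuation are tabulated over the whole study, and MAAEs to 6 months. Overlapping or consecutive events of the same preferred term that begin in the active period stay there. One Table 4 interval runs through delivery, and all collected AEs are listed. What remains exposed is mainly unsolicited AEs that are non-serious, not medically attended, and start after delivery but within 28 days. None of these displays gives the 28-day unsolicited-AE endpoint itself, and the Table 4 interval through delivery varies in length between women.

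Deleting rule (f) is not the answer: Post-dose 1 would then overlap Postpartum follow-up 1 and one AE could sit in both.

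**Conclusion.** The concern holds as an unreconciled conflict between Table 3 and the 28-day definitions in Sections 5.3.1 and 5.6.1.3. If the 28-day tables are built from Post-dose 1, the window is shortened for every delivery or termination within 28 days of vaccination, including term births after late vaccination, with no adjustment in the denominator. The 11-44% for the 28-38 week stratum rests on evenly spread vaccination and delivery at 37-41 weeks, so it is a range under assumptions and not an estimate for this trial.

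The study is descriptive, and the document does not support a claim that events are lost from it. The harm is an ambiguous primary unsolicited-AE table and an uninformative Post-dose 1 outcome column.

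The Entire Study label in Table 4 is a separate drafting fault. Read literally, it leaves Groups 1 to 3 without that interval. A reader might infer that they have no whole-study SAE or AESI tables, but Section 5.6.1.3 makes the intent clear, and the component end dates of the Primary Vaccination Period can be derived for those groups.

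**What to change.** 1. Keep rule (f) in Table 3 for the prepartum/postpartum split.
2. Add a Table 4 interval from first vaccination to 23:59 on day +28 irrespective of delivery, still ending earlier at last contact, data cut-off, booster or an outside COVID-19 vaccine.
3. State that the 28-day unsolicited-AE tables use this interval. Use it also for a supplementary count of pregnancy outcomes within 28 days of vaccination.
4. Leave the whole-study SAE and AESI tables unchanged; a 28-day limit there would contradict Section 5.3.1.
5. State in Section 5.4.3 that births and losses are not reported in the Post-dose 1 phase column.
6. Separately, define Entire Study in Table 4 for all groups.

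The cost is SAP wording and one derived interval in the analysis datasets. No new data are needed, because the endpoint already covers 28 days. The change should be made before the primary analysis tables are produced.
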